6.4.2 Study Stopping Criteria

If any of the following occur, no further administration of investigational product will take place and no further subjects will be entered into the study:

1. The incidence or severity of adverse events in this or other studies indicates a potential health hazard to subjects in the current study, determined after review of relevant information through internal MedImmune safety data review procedures.
2. Subject enrollment is unsatisfactory.
3. Non-compliance that might significantly jeopardize the validity or integrity of the study.
4. Sponsor decision to terminate development.

In case a safety event requiring enrollment suspension occurs, a prompt cumulative review of safety data and the circumstances of the event in question will be conducted by the medical monitor and the MedImmune safety review committee to determine whether dosing and study entry/randomization should be resumed, whether the protocol will be modified, or whether the study will be discontinued permanently. The relevant competent health authorities in participating countries and IRB/IEC will be notified of any event that triggers suspension of enrollment in this study. If the study is suspended for safety reasons and it is deemed appropriate by the sponsor to resume the study, approval from the relevant regulatory authorities (and IRBs/IECs when applicable) will be obtained prior to resuming the study.

Decisions regarding ongoing treatment for any subjects who have already received investigational product and are currently in the study at the time study-stopping criteria are met will be made on a case-by-case basis after discussion with the subject, principal investigator, and the sponsor. In the case that a safety event requiring enrollment suspension

occurs, all subjects on treatment will be re-consented. Regardless of whether dosing is continued or not, all subjects who were on treatment at the time study-stopping criteria were met will continue to be followed by the principal investigator for safety until the end of the study.

Withdrawal criteria for individual subjects are provided in Section [6.4.1](#).

6.4.3 Monitoring of Dose Administration

Arm A

Vital signs will be evaluated prior to infusion and at the end of infusion only; additional monitoring may be performed if clinically indicated. Vital signs include temperature, blood pressure, pulse rate, respiratory rate, and pulse oximetry.

As with any antibody, allergic reactions to dose administration are possible. Therefore, appropriate drugs and medical equipment to treat acute anaphylactic reactions must be immediately available, and study personnel must be trained to recognize and treat anaphylaxis.

In the event of an IRR, the infusion of MEDI-551 may be decreased by 50% or interrupted until resolution of the event (up to 4 hours) and re-initiated at 50% of the initial rate until completion of the infusion. Acetaminophen and/or an antihistamine (eg, diphenhydramine), or institutional equivalents, may be administered at the discretion of the investigator. If the infusion reaction is severe or prolonged, methylprednisolone 100 mg (or the equivalent) should be administered as well. For subsequent infusions in subjects who experience an IRR and do not require discontinuation of MEDI-551 (see Section [6.4.1](#)), acetaminophen and an antihistamine may be administered prior to initiation of the MEDI-551 infusion. If a subject experiences a Grade 3 IRR, all subsequent administration of MEDI-551 must be preceded by IV methylprednisolone 100 mg (or the equivalent) 30 minutes prior to initiation of MEDI-551 infusion.

Arms B, C, and D

Vital signs are evaluated prior to infusion and at the end of infusion as well as at the EOT and 90-Day Post Last Dose visits; additional monitoring may be performed if clinically indicated.

As described in Section [6.4.1](#), all subjects receiving MEDI-551 in Arms B, C, and D must receive mandatory premedication consisting of a minimum dose of 60 mg IV

methylprednisolone (or its equivalent), 500 to 650 mg oral acetaminophen (or paracetamol equivalent), and 50 mg IV diphenhydramine (or its equivalent) before the initial MEDI-551 infusion on Day 1 of Cycle 1 in Arms B and D, and on Day 2 of Cycle 1 in Arm C.

In the event of an IRR, the infusion of MEDI-551 may be interrupted until resolution of the event (up to 4 hours) and re-initiated at the 1 mL/minute rate. The rate may be slowly increased by 50% every 15 minutes until completion of the infusion. If the infusion reaction is severe or prolonged, methylprednisolone 100 mg (or the equivalent) may be administered in addition to acetaminophen (or institutional equivalent) and/or an antihistamine at the discretion of the investigator for management of the IRR ([Simons, 2010](#); [Sampson et al, 2006](#)). In the event of a Grade 4 IRR, the subject should have MEDI-551 permanently discontinued (see Sections [4.5.2.1](#) and [4.5.6](#)).

If a subject experiences a Grade 3 IRR and does not require permanent discontinuation of MEDI-551 (see Sections [4.5.2.1](#) and [4.5.6](#)), all subsequent administration of MEDI-551 must be preceded by IV methylprednisolone 100 mg (or the equivalent), oral acetaminophen 500 to 650 mg (or equivalent dose of paracetamol), and IV diphenhydramine 50 mg 30 to 60 minutes prior to initiation of MEDI-551 infusion. Subjects who only experience a Grade 1 or 2 IRR and do not require permanent discontinuation of MEDI-551 (see Section [4.5.2.1](#)) may receive methylprednisolone (or the equivalent), acetaminophen (or paracetamol equivalent), and diphenhydramine 30 to 60 minutes prior to initiation of the MEDI-551 infusion at the investigator's discretion.

Monitoring of the administration of rituximab in Arm C will be performed according to institutional protocols.

As with any antibody, allergic reactions to dose administration are possible. Therefore, appropriate drugs and medical equipment to treat acute anaphylactic reactions must be immediately available, and study personnel must be trained to recognize and treat anaphylaxis.

7 STATISTICAL CONSIDERATIONS

7.1 General Considerations

Data will be provided in data listings sorted by treatment group and subject number. Tabular summaries will be presented by treatment group. Categorical data will be summarized by the number and percentage of subjects in each category. Continuous variables will be summarized by descriptive statistics, including mean, standard deviation, median, minimum, and maximum. Details of endpoint analyses will be described in the statistical analysis plan.

7.2 Analysis Populations

The **Evaluable population for DLT** will include all subjects in the dose-escalation phase who receive at least 1 full cycle of MEDI-551 and complete safety follow-up through the DLT evaluation period (defined in Section 4.5.6) or experience any DLT during the DLT evaluation period. The Evaluable population for DLT will be used for the MTD analysis.

The **Safety population** will include all subjects who receive any treatment of MEDI-551. The Safety population will be used to evaluate baseline characteristics as well as all endpoints for safety.

The **Evaluable population for efficacy** will include all subjects who receive any treatment of MEDI-551 and complete at least one post-baseline disease assessment. The Evaluable population for efficacy will be used to evaluate the efficacy endpoints.

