Once an MTD was identified or the maximum planned dose not exceeding the MTD was reached, additional subjects were to be enrolled and treated at the selected dose of MEDI-551 in combination with rituximab in the dose-expansion portion of this arm to ensure a total sample size of 26 efficacy evaluable subjects were available for analysis after completing one post-treatment disease evaluation. The 26 subjects were to include subjects treated at the selected dose during the dose-escalation portion of this arm. Treatment may continue until the subject experiences unacceptable toxicity, disease progression, withdraws consent, or achieves a CR (2 additional cycles of MEDI-551 at the same dose may be administered before EOT). A total of 19 subjects were enrolled in Arm C.

Subjects in Arm C were stratified based on their responsiveness to any prior anti-CD20-based therapy with the option of ensuring a minimum number of 7 subjects who are refractory to any prior anti-CD20-based therapy are enrolled if clinical data from Arm D or emerging preclinical data suggest that the combination of anti-CD20 and anti-CD19 therapies improve response in this subpopulation.

[figure not shown]

Figure 3.1-3 Flow Diagram for Dose Escalation and Expansion in Arm C

MTD = maximum tolerated dose.

Arm D

Enrollment in Arm D is complete. Given the high unmet medical need in patients with refractory aggressive lymphoma and in light of preservation of CD19 expression on the surface of these malignant cells, MEDI-551 may represent a salvage therapy option for anti-CD20-refractory patients. Evidence of clinical activity and safety of MEDI-551 in an unselected patient population (Arm A) supported investigating MEDI-551 in the anti-CD20-refractory population. Arm D evaluated the clinical activity of MEDI-551 in subjects with any anti-CD20-refractory aggressive lymphoma (refractory DLBCL, Grade 3b FL, FL transforming to DLBCL, and MCL). A flow diagram for Arm D is provided in [Figure 3.1-4](#).

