Evaluations	Day 1, All Cycles Once Version 13.0 Is In Effect (± 7 Days)	EOT Visit (± 7 Days)	EOS or 90-Day Post Last Dose Visit (± 7 Days)
Verify eligibility criteria	X		
Medical history	X		
Concomitant medications	X	X	X
Pregnancy test (females of childbearing potential)	X		
Karnofsky performance status	X	X	X
Physical examination (focused)	X	X	X
AE/SAE assessment	X	X	X
Weight	X	X	
Vital signs	Pre and post dose	X	X
ECG (single)		X	X
Serum chemistry	X	X	X
Hematology	X	X	X
Coagulation tests		X	X
Urinalysis		X	X
Quantitative IgM, IgG, IgA		X	X
Flow cytometry of whole blood for T/B cell and effector cell subsets		X	X
MEDI-551 serum concentrations		X	X
Anti-MEDI-551 antibodies		X	X
Disease assessment ^a	Every 2-6 months	X ^b	
MEDI-551 administration	X		

AE = adverse event; ECG = electrocardiogram; EOS = End of Study; EOT = End of Treatment; Ig= immunoglobulin; SAE = serious adverse event;

^a Subjects with FL, DLBCL, MCL, and transformed indolent lymphoma: Assess by CT scan (FDG-PET or PET-CT if clinically indicated) and physical exam every 2 months during the first year of treatment and then every 6 months. Additional scans may be performed if clinically indicated. Subjects with CLL “(including SLL)” will perform chest, abdomen, pelvis, and neck (if applicable). CT scans are only required after the first year of treatment if clinically indicated (eg previous indication to treat was based on predominantly nodal disease) or if indicated based on hematology findings.

^b Disease assessment not required if performed within 8 weeks prior to the EOT visit.

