- **Progression-free survival:** Progression-free survival will be measured from start of MEDI-551 administration until the first documentation of PD/relapse or death, whichever occurs first. Progression-free survival will be censored on the date of last disease assessment for subjects who have no documented PD/relapse or death prior to data cutoff, dropout, or the initiation of alternative anticancer therapy.
- **Overall survival:** Overall survival will be determined as the time from the start of MEDI-551 administration until death. For subjects who are alive at the end of study or lost to follow-up, OS will be censored on the last date when subjects are known to be alive.

The analysis methods will differ by the types of endpoints. For categorical endpoints, proportions will be summarized, 80% and 95% confidence intervals will be calculated using the Clopper-Pearson exact method. For time-to-event endpoints, Kaplan-Meier method will be used to describe the endpoints graphically and to estimate the median or the event rates at time of interest.

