A total of 7 subjects were enrolled in Arm B; all were in dose escalation (n = 3 each for 6 and 12 mg/kg, n = 1 for 24 mg/kg). Based on emerging PK and pharmacodynamic data, a dose of 12 mg/kg, administered weekly during Cycle 1 and then monthly in subsequent cycles, was determined to be sufficient to saturate the B-cell sink and achieve full exposure. At the sponsor's discretion and not due to any safety issues, no further dose-escalation was conducted. The MTD was not reached.

Arm C dose escalation was completed as planned, with 3 subjects each in the 8 and 12 mg/kg cohorts.

Dose Expansion

A sample size of 26 subjects was planned for each dose-expansion cohort in Arms B and C. Given an expected response rate of 50% for both cohorts, this would provide 80% power at a significance level of 0.20 (2-sided) to exclude the historical response rate of 30%, and associated 80% confidence intervals for the response rate would have a precision of $\pm 13\%$. The 30% historical response rate was selected for both Arms B and C expansion cohorts based on the following reported data:

- In relapsed CLL patients, OR rates between 15% and 30% were reported for rituximab monotherapy ([O'Brien et al, 2001](#); [Mavromatis and Cheson, 2003](#)).
- In DLBCL patients with 2 prior lines of therapy, response rates were only about 30% with single-agent rituximab ([Coiffier et al, 1998](#); [Wang et al, 2013](#); [Churpek et al, 2013](#)).

Enrollment in Arm B was discontinued prior to dose expansion at the sponsor's discretion and not due to any safety issues..

Further enrollment in Arm C was halted at the sponsor's discretion (and not due to any safety issues) after enrollment of 19 subjects (3 in the 8 mg/kg MEDI-551 cohort and 16 who received 12 mg/kg MEDI-551). Of the 19 subjects there were only 7 responders, and there was about a 13% probability of meeting the protocol-specified target response rate of 50%.

Arm D

A sample size of approximately 26 subjects was planned for Arm D. Given an expected response rate of 50% for this cohort, this would provide 80% power at a significance level of 0.20 (2-sided) to exclude the historical response rate of 30% ([Zinzani et al, 2013](#); [Witzig et al, 2011](#)), and associated 80% confidence intervals for the response rate would have a precision of $\pm 13\%$.

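### Section 7.2 restricts every efficacy endpoint to treated subjects with a post-baseline disease assessment, which inflates response rates and keeps the earliest deaths out of PFS and OS

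*Protocol*

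**What the plan says.** Protocol Section 7.2 defines the Evaluable population for efficacy as the set that "will include all subjects who receive any treatment of MEDI-551 and complete at least one post-baseline disease assessment". It adds, with no exception, "The Evaluable population for efficacy will be used to evaluate the efficacy endpoints". The all-treated set has a different job: "The Safety population will be used to evaluate baseline characteristics as well as all endpoints for safety".

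Section 7.3 lists objective response, PFS and OS as primary endpoints in Arms B, C and D and as secondary endpoints in Arm A. Section 7.4.3 then defines the two time-to-event endpoints from first dose:

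- PFS: "Progression-free survival will be measured from start of MEDI-551 administration until the first documentation of PD/relapse or death, whichever occurs first".
- OS: "Overall survival will be determined as the time from the start of MEDI-551 administration until death".

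The same conditioning enters the sample size. For Arms B and C, Section 3.1 aims to ensure that "26 efficacy evaluable subjects were available for analysis after completing one post-treatment disease evaluation". Section 7.5 claims for that number "80% power at a significance level of 0.20 (2-sided) to exclude the historical response rate of 30" percent, given an expected rate of 50%.

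No section exempts PFS or OS from the population rule, counts unassessed subjects as non-responders, or treats death before assessment as an assessment.

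**The concern.** Two separate biases follow from the one rule, and both flatter the drug.

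**Response.** A treated subject who dies, withdraws or is lost before any assessment adds nothing to the numerator. Dropping that subject shrinks only the denominator. The cohorts have no concurrent control and are set against an external 30%, so nothing offsets the rise.

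**PFS and OS.** Entry to the analysis depends on reaching an assessment that comes after time zero. A death before that point is an event under Section 7.4.3 but cannot be counted under Section 7.2. The reported curves therefore omit the earliest deaths. Eligibility asks for a life expectancy of only 12 weeks or more, in relapsed or refractory disease, so such deaths are plausible.

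The concern has limits. Stopping the drug early does not by itself exclude a subject, since the current schedule (Table 5.2.1-1) has a disease assessment at end of treatment, waived only under footnote b: "Disease assessment not required if performed within 8 weeks prior to the EOT visit". Early withdrawals without an event need not bias PFS or OS. Time to response and the duration endpoints are confined by definition to subjects who have been assessed, so the rule does not change them.

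**Working it through.** **Inputs from the protocol.** Planned n = 26, null rate 30%, expected rate 50%, two-sided alpha 0.20, stated power 80% and precision ±13 points (Section 7.5); exact Clopper-Pearson 80% intervals (Section 7.4.3); 7 responders of 19 in Arm C and 3 of 16 in Arm D (Section 7.5). **Assumed:** the unassessed share f, shown from 5% to 20%.

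**1. The plan's own figures.**
- Power by normal approximation, 0.10 per tail: Φ[(√26 × 0.20 − 1.2816 × √(0.3 × 0.7)) / √(0.5 × 0.5)] = Φ(0.865) = 80.6%. This matches the stated 80%.
- Half-width of the 80% interval at 50%: 1.2816 × √(0.25/26) = 12.6 points. This matches ±13.
- Probability in Arm C of a true rate of at least 50%, flat prior and 7/19: 0.132. This matches the stated 13%. With 7/17 it would be 0.24. The halting calculation is therefore consistent with all 19 enrolled subjects as denominator, not a reduced set.

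**2. Effect on the response rate by design.** If a share f of treated subjects is never assessed and none of them can respond, the rate among evaluable subjects is 0.30/(1 − f) when the all-treated rate is 30%. The protocol gives no cut-off. The smallest count out of 26 whose exact 80% lower limit exceeds 30% is 12 (12/26: 32.4%; 11/26: 28.9%).

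| f | Apparent rate at true 30% | P(at least 12 of 26) |
|---|---|---|
| 0 | 30.0% | 6.0% |
| 5% | 31.6% | 8.5% |
| 10% | 33.3% | 12.1% |
| 15% | 35.3% | 17.0% |
| 20% | 37.5% | 23.7% |

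The 12/26 cut-off has exact power of 72.1% at 50%. Taking 11/26 instead gives 83.7% power, with one-sided error of 12.5% already at f = 0.

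**3. Effect on the actual counts**, if k non-responders were never assessed (k is assumed).

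| k | Arm C | 80% lower limit | Arm D | 80% lower limit |
|---|---|---|---|---|
| 0 | 7/19 = 36.8% | 21.8% | 3/16 = 18.8% | 7.1% |
| 1 | 7/18 = 38.9% | 23.1% | 3/15 = 20.0% | 7.6% |
| 2 | 7/17 = 41.2% | 24.6% | 3/14 = 21.4% | 8.1% |
| 3 | 7/16 = 43.8% | 26.3% | 3/13 = 23.1% | 8.8% |
| 4 | 7/15 = 46.7% | 28.2% | not shown | not shown |

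Neither arm excludes 30% in this range. Arm C would need 5 unassessed (7/14, lower limit 30.5%).

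**4. Effect on PFS and OS.**
- Simple count, for illustration: if 2 of 19 die before assessment and no one else has yet died, true survival is 17/19 = 89.5%, but the plan would show 17/17 = 100%.
- Median: suppose a share f dies before any assessment, and before the all-treated median, and the rest follow an exponential curve with reported median m. The all-treated median is m × log₂[(1 − f)/0.5]. With m = 12 months (assumed), f = 10% gives 12 × log₂(1.8) = 10.2 months and f = 20% gives 12 × log₂(1.6) = 8.1 months.

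**The case against.** The strongest objection is that the effect may be nil in practice. The documents do not show a single subject dropped from a denominator. The rates the protocol reports use enrolled or treated subjects: 7/19, 3/16 and, in Section 1.4, 30/111. The Arm A groups quoted in Section 1.5 (26 CLL, 34 FL, 26 DLBCL) are no smaller than expansion enrolment (24, 23, 21). Karnofsky and life-expectancy criteria also limit early death. This stands as a limit on size, and the 20% end of the range has no anchor in the documents. It does not alter what Section 7.2 prescribes for the analyses still to be reported.

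Several points limit the illustrations:

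- No cohort reached 26, so the error rates in step 2 describe the design, not a test that will be run.
- Arm C's 19 pool 3 subjects at 8 mg/kg with 16 at 12 mg/kg. The planned 26 were at the selected dose, and responders among the 16 are not given.
- Table 5.2.1-1 is the Version 13.0 schedule, so it cannot show what early dropouts were offered under earlier versions.
- The denominators behind the 30% benchmark are not in the documents. If those studies used evaluable patients, the evaluable set would be the closer comparison for response.

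It can also be said that response-evaluable sets are common in early-phase work, that this one agrees with how Arms B and C were sized, and that endpoint details belong to the statistical analysis plan. As a supportive set for response, that is reasonable. It does not carry over to OS, which needs no disease assessment. Section 7.2 itself fixes the population, so the point is not one left open for later.

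**Conclusion.** The concern holds and should be fixed. As written, Section 7.2 removes unassessed non-responders from every response denominator and keeps deaths before first assessment out of PFS and OS, against the definitions in Section 7.4.3. The direction is certain for response, which can only rise. For PFS and OS the distortion is upward whenever a subject dies before any assessment.

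The size depends on a number the documents do not give. It is zero if every treated subject was assessed. Under the assumed ranges, the reported rate gains 2.1 to 9.9 points in Arm C (1 to 4 unassessed) and 1.2 to 4.3 points in Arm D (1 to 3 unassessed; differences of the rounded rates above). What is affected is the reported estimates. The decisions to halt Arms C and D rested on all enrolled subjects and are not touched, and neither arm would exclude 30% within these ranges.

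**What to change.** In Section 7.2, make all treated subjects (the existing Safety population) the primary set for CR, objective response, disease control, PFS and OS. Count a subject with no post-baseline assessment as a non-responder, and count a death before any assessment as a PFS and OS event.

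In Section 7.4.3, add that a subject with no post-baseline assessment and no death is censored for PFS at first dose. The present rule censors at the last disease assessment and does not cover a subject who has none after baseline.

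Keep the Evaluable population for efficacy as a sensitivity analysis and report, for each arm, how many treated subjects it leaves out.

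The cost is one paragraph in Section 7.2, one sentence in Section 7.4.3, and tables run on a population that already exists. No new data are needed. Response rates may come out slightly lower, and they would be on the same footing as the 7/19, 3/16 and 30/111 the protocol already quotes.

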7.3 Endpoints

The primary, secondary, and exploratory endpoints are listed in this section, and assessment of the endpoints is described in Section 7.4.

7.3.1 Primary Endpoints

Arm A

1. MTD or OBD: DLTs
2. Safety: AEs, SAEs, laboratory evaluations, vital signs, physical examinations, and ECGs

Arms B and C

1. MTD is defined as the highest dose where ≤ 1 out of 6 subjects experience a DLT during the DLT evaluation period or the highest protocol-specified dose not exceeding MTD:
DLTs
2. Safety: AEs, SAEs, laboratory evaluations, vital signs, physical examinations, and ECGs
3. Clinical activity/efficacy: CR, duration of CR, PR, objective response, disease control, TTR, duration of objective response, duration of disease control, PFS, and OS

Arm D

1. Clinical activity/efficacy: CR, duration of CR, PR, objective response, disease control, TTR, duration of objective response, duration of disease control, PFS, and OS

